Interim Analysis	10
Statistical Analysis	10
REFERENCES	11

RATIONALE

Globally, it is estimated that over 200 million people each year require mechanical ventilation using an endotracheal tube, as part of general anesthesia for surgery or as a lifesaving intervention in critical illnesses (for example, in severe respiratory failure due to pneumonia).^{1,2} Once a patient has recovered, the endotracheal tube is removed, a process called 'extubation'. While routinely performed, extubation is a skilled and potentially high-risk procedure that should be performed only when physiologic, pharmacologic, and contextual conditions are optimal.³ The decision of when and how to extubate a patient can be challenging because optimizing certain conditions can antagonize others. For example, extubation while the patient is fully anesthetized before upper airway reflexes return prevents laryngospasm but increases the risk of aspiration. Complications at this stage of patient care can result in decreased oxygen delivery to the brain and body, sometimes leading to serious adverse events such as cardiac arrest, brain damage, or death.⁴ Indeed, in audits and safety reports, one quarter of airway complications that result in death or brain death occur at the time of extubation.⁵ Each of the last 5 semi-annual safety bulletins of critical care incidents in England report serious adverse complications of extubation resulting in patients' death. 6-8 In all these cases, the experts' opinion reflected that these complications could have been prevented with proper planning and timing, adequate techniques and expertise at the bedside.9

Despite the frequency of extubation and the potential for life-threatening complications of extubation failure, we currently lack systematic data on the rate and circumstances under which these severe complications occur.³ The limited data on complication rates indicate 10-30% of extubations may lead to severe complications, depending on the population and outcome definition.^{5,10-16} However, the certainty of these estimates is severely limited because they are based on studies that are small,¹¹ mostly single-centre, based on clinician recall,^{5,10} only capture a small portion of extubation complications,¹⁴ or do not reflect current clinical practice.¹² Beyond these data, extubation complications and practices have not been thoroughly studied.⁴ Yet extubation management decisions and outcomes depend on a complex interplay of patient and situational characteristics,⁴ so a large, systematic study would be required to make conclusions about the best extubation technique in various patient populations and settings.¹⁷

Historically, extubation has received significantly less research attention than intubation¹⁷⁻²⁰ (i.e., the process of inserting the endotracheal tube at the start of mechanical ventilation), even though complications at extubation may occur as frequently as complications at intubation, but may have increased risk of severe patient harm.^{6-8,12,18,21-25}

Promisingly, a recent focus on intubation complications, risk factors, and best-practices has decreased intubation related complications 26 – an evidence-based bundle of intubation strategies decreased airway complications by $26\%^{27}$ – suggesting that a similar program of research focusing on extubation could have a comparable impact on patient safety and outcomes. 28

As a result, there have been calls for research to identify risks of extubation complications and effective extubation techniques.^{5,7,19,20,28-30} In particular, high quality baseline data on complication rates are needed to evaluate future interventions and clinical practice

guidelines.³¹ High quality data on patient risk factors for complications are needed because current guidelines specify that extubation algorithms should be selected based on patient risk level, but risk factors to date are based mainly on expert opinion. The algorithms themselves are based on case studies and expert opinion as there has been no large-scale study of the effectiveness of individual extubation techniques or guidelines,^{4,20,28} so procedural factors associated with complications need to be elucidated. While adherence to clinical practice guidelines has not been formally evaluated, surveys of anesthesiology and critical care professionals show non-adherence to some best practices and considerable variation in practice.^{5,10,32} Lack of adherence to best practices is frequently at the root cause of serious adverse outcomes of extubation, according to data from audits and medicolegal claims, suggesting that half of the complications are preventable.^{17,23,24} For example, half of adverse events associated with extubation in a large audit had evidence of poor planning.¹⁷ Therefore, data on the frequency and nature of extubation complications, patient and procedural risk factors for complications, and guideline adherence rates are needed before these preventable events can be addressed.

We propose the EXTUBE study, the first systematic, large, international prospective cohort study evaluating the incidence, risk factors, and outcomes of extubation-related complications and describing clinical practices related to extubation. We will use an innovative, point prevalence design that we recently adopted to successfully conduct the INTUBE study – the largest ever study on endotracheal intubation in critically ill patients.³³ These data will provide a precise understanding of current extubation practices and associated complications, and will be fundamental in informing targeted interventions to improve patient safety.

METHODS

Study Design

EXTUBE is an international, multicentre, prospective observational point prevalence study in patients who require extubation after general anesthesia or after critical illness in the operating room (OR), out of OR anesthesia location or intensive care unit (ICU). This study is designed according to the Strengthening the Reporting of Observational Studies in Epidemiology (STROBE) Statement guidelines.³⁴

Study Centres

To meet our target sample size (n=3,000), we have established a network of at least 60 broadly representative academic and non-academic hospitals worldwide that will report on patient data for this study. We will collect information about each study centre at the time of enrollment (e.g., community vs academic hospital, unit type [ICU, post-anesthesia care unit], number of beds in the hospital, number of beds in the unit). Each centre will be assigned a two-week enrollment window between January 2025 to December 2026, during which they will collect data on all eligible patients up to a maximum of 50 patients per centre.

Any future collaborations and transfer of data from/to UHN will be submitted for Research Ethics Board (REB) review via future amendment submission.

Patients

All potentially eligible patients will be identified by local investigators by screening all inhospital extubations occurring in the ORs, out of OR anesthesia locations and ICUs during the enrollment window. Potentially eligible patients undergoing general anesthesia will be identified by screening daily preoperative assessment clinic lists, operating room booking lists, incoming patient lists on surgical wards, and monitoring operating room and out of OR procedure lists for add-on surgeries cases. Potentially eligible patients in the ICU will be identified by screening ICU census lists.

Inclusion Criteria

All adult patients (≥18 years old) undergoing extubation of an endotracheal tube (including index extubation and re-extubations) after general anesthesia in the OR, out of OR anesthesia location or ICU during the specified enrollment window will be included.

Exclusion Criteria

Patients will be excluded if the extubation is:

- (i) performed in the context of withdrawal of life support measures or
- (ii) performed for tracheostomy decannulation.

For each patient who is not included, reasons for exclusion will be reported.

Ethical Considerations

The study will be conducted in accordance with Good Clinical Practice guidelines³⁵ and the Declaration of Helsinki.³⁶ Additionally, the research will be conducted in compliance with local REB requirements at each centre.

We are requesting a waiver of consent (i.e., patient consent is not requested for their data to be included in this study). This study satisfies all of the criteria for alteration to consent as outlined in Article 3.7a of the Tri-Council Policy Statement on the Ethical Conduct for Research Involving Humans.³⁷ First, the research involves very minimal risk to patients as this is an observational study where patient care will not be modified, data will be collected from routine data sources, and patients will not be contacted. Second, waiver of consent will not affect the welfare of the patient. Third, this research question, which is fundamental to improve patient safety, is best answered with a waiver of consent, as collecting all consecutive patients are needed to provide an unbiased estimate of the prevalence of complications and asking for consent would make this impossible. Overall, the potential benefits of conducting this study outweigh the foreseeable risks to patients.

Data Collection

Data will be collected on paper case report forms (CRFs). Local investigators are expected to transcribe all collected data into an internet-based electronic CRF (eCRF, Research Electronic Data Capture – REDCap). Each local investigator will be trained in how to use the eCRF and will receive a personalized username and password. Each patient will be coded through a patient identification number (PIN) generated by the eCRF and no patient names or initials will be present on the paper CRF. Data will be handled confidentially and the paper CRF

will be stored behind a lock at each local site. Each centre should keep data stored for the length of the study and the time foreseen by local rules but at least 10 years from the date of study completion.

Data Quality and Security

To ensure data quality, training sessions will be provided to all research personnel involved in the trial. Standardized case report forms will be created in REDCap for collecting outcome data, with real-time checks for validity and completeness. To maximize usability and minimize missing data, the eCRF will use branching logic. To minimize missing data, the eCRF cannot be submitted with missing data. Coordinating centre personnel will perform quality checks on all data as it is received to screen for and verify potentially erroneous data (e.g., outliers) and review monthly reports of data quality and completeness. To ensure we capture all eligible patients during the enrollment window, we have included investigators from anesthesia and critical care at each study centre, and each day, we will record reason for exclusion for every patient in the ICU and undergoing general anesthesia who is not included in the study.

Data will be stored in a password-protected, encrypted, database on UHN's validated REDCap server. All patients will be identified in the database by a unique study ID. Identifying information will be encrypted and stored in a separate database.

OUTCOME MEASURES

Primary Outcomes

The *primary outcome* will be the occurrence of at least one of the following (composite outcome) occurring within 60 minutes after the end of extubation:

- Severe hypoxemia (oxygen saturation as measured by pulse oximetry falls below SpO2 < 80% for > 5 minutes)
- ii. Cardiac arrest
- iii. Need for airway management (reintubation, insertion of a supraglottic airway, bag-mask ventilation).

Secondary Outcomes

Secondary outcomes will include the new occurrence of the following complications within 60 minutes of extubation:

- i) Difficult airway (i.e., experienced difficulty by an experienced airway manager with any or all of laryngoscopy or tracheal intubation, supraglottic airway use, face-mask ventilation, or front-of-neck airway) and complications related to airway management (e.g., esophageal intubation) if reintubation is required,
- ii) Planned and unplanned non-invasive respiratory support or high flow nasal cannula
- iii) Emergency front of neck airway
- iv) Cardiac arrhythmia requiring chemical or electrical treatment
- v) Severe hypotension (systolic arterial pressure < 65 mmHg recorded at any time or systolic arterial pressure < 90 mmHg for > 30 minutes or new need/increase of vasopressor and/or fluid load > 15 mL/kg)
- vi) Severe hypertension (systolic blood pressure ≥180 mmHg and/or diastolic blood pressure ≥120 mmHg),
- vii) Aspiration of gastric contents (gastric contents inhaled into the larynx and the respiratory tract),
- viii) Pneumothorax/pneumo-mediastinum,
- ix) Dental injury (notable change to the patient's dentition attributable to extubation or to reintubation, should this be required),
- x) Airways injury (e.g., vocal cord damage, arytenoid dislocation).

We will also collect the following outcomes:

- xi) In-hospital mortality within 7 days after extubation
- xii) Re-intubation within 48 hours of extubation

STATISTICAL ANALYSIS

Sample Size and Number of Study Centres

The sample size calculation is based on the primary objective (to estimate the incidence of immediate complications related to extubation in adult patients after general anesthesia and/or after critical illness). Based on estimates from current literature, ⁶⁻⁸ we expect an incidence of such complications around 8% (80 per 1,000 patients). Assuming such incidence, 2,827 patients need to be included to estimate a 95% confidence interval not wider than 2% (20 per 1,000 patients). Assuming approximately 5% of patients will be missing primary outcome data, we aim to collect data on 3,000 patients to meet our target sample size of 2,827. This sample size will also allow the inclusion of 15-22 candidate factors in the secondary objectives (i.e., investigation of the risk factors for the occurrence of the primary outcome).

Since we aim to estimate the overall incidence of the primary outcome in the population of interest (rather than the expected incidence in a centre), all eligible patients could be included during the enrollment window without any limitations on the number of enrolled patients in each centre. We estimate we will need to recruit at least 60 centres to achieve the target sample size, assuming an average of 50 extubation procedures in each centre in the

enrollment window. If the number of extubations per centre is lower than anticipated, we will continue to recruit centres until we reach our target sample size.

Interim Analysis

We plan an interim analysis with the data from the first 10 centres to complete their enrollment window to check if the magnitude of the primary outcome is broadly in line with the expected incidence. If the real incidence is different than expected incidence, or if we observe marked difference between populations in the OR and in the ICU, the sample size calculation may be updated, and the number and type of participating centres may be increased and diversified as needed. As this is an observational study, the interim analysis will not drive decisions about stopping for harm or futility.

Statistical Analysis

Descriptive statistics will be used to describe the patient characteristics. Continuous data will be expressed as mean and standard deviation or median and interquartile range, and categorical data as number and percentage. Bivariable analyses will be conducted using $\chi 2$ or Fisher exact test for categorical variables, and the Mann-Whitney or t test for continuous variables. A complete case analysis (with no assumptions made for missing data) will be performed. For the primary objective, the incidence of primary and secondary outcome measures (with 95% confidence interval) will be estimated overall, and within clinically relevant strata (e.g., sex, age, extubation in OR vs. ICU, low vs. high-risk extubation, global region, comorbidities, indication for intubation, complications at the time of original intubation, etc.).

For secondary objectives, (1) to identify risk factors for post-extubation complications, multivariable models (which may include logistic regression, Poisson regression, negative binomial regression, according to the nature of the data) adjusting for patient and surgical characteristics will be conducted. (2) Kaplan-Meier curves and Cox regression may be implemented to analyze survival data, if appropriate. (3) Exploratory analysis will be conducted to understand the current practice related to extubation and adherence. Given the multicentre enrollment, all analyses will be performed using multi-level models (with patients nested within study centre). All tests will be 2-sided and a p-value less than 0.05 will be considered statistically significant. Statistical analysis will be performed using R software (R Foundation for Statistical Computing, Vienna, Austria).

REFERENCES

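### The inclusion criterion leaves out the critical-illness group that the Study Design and the primary objective both name

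*Protocol*

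**What the plan says.** The protocol defines its population in three places.

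- **Study Design:** "patients who require extubation after general anesthesia or after critical illness in the operating room (OR), out of OR anesthesia location or intensive care unit".
- **Sample Size and Number of Study Centres**, stating the primary objective: "to estimate the incidence of immediate complications related to extubation in adult patients after general anesthesia and/or after critical illness".
- **Inclusion Criteria**, limited to adults within a centre's assigned window: "undergoing extubation of an endotracheal tube (including index extubation and re-extubations) after general anesthesia in the OR, out of OR anesthesia location or ICU".

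The first two name critical illness as a second route into the study. The third keeps the anesthesia route and the same three locations, and drops the second route.

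Other sections bear on intent. Under Patients, there are two screening streams: "Potentially eligible patients undergoing general anesthesia will be identified by screening daily preoperative assessment clinic lists" (with OR and procedure lists), and "Potentially eligible patients in the ICU will be identified by screening ICU census lists". The first exclusion is an extubation "performed in the context of withdrawal of life support measures or"; the second is tracheostomy decannulation. Under Data Quality and Security, "we will record reason for exclusion for every patient in the ICU and undergoing general anesthesia who is not included in the study". Statistical Analysis plans strata that include OR versus ICU and indication for intubation. Interim Analysis allows the sample size and the mix of centres to change if the OR and ICU populations differ markedly.

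**The concern.** The inclusion criterion is the sentence a site applies to decide who enters. The Rationale separates ventilation given as part of anesthesia for surgery from ventilation given as a lifesaving measure in critical illness, with severe respiratory failure from pneumonia as its example. By that distinction, a patient like the one in the example does not meet the criterion unless general anesthesia was also given.

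With at least 60 centres, some could follow the sentence and others the evident intent. Case mix would then vary between centres for a reason unrelated to their patients. That would affect the overall incidence, the OR and ICU strata, the risk-factor models and the between-centre variation in the multilevel models. It would also affect the interim comparison that may prompt a change in sample size. A shortfall need not show in the total, because centres are added until the target is reached. The request for a consent waiver argues that consecutive capture is needed for an unbiased estimate, and a criterion open to two readings weakens that argument. Each centre has a single two-week window, so prospective capture is lost once it closes.

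**Working it through.** **1. The text.** The location list in the criterion can attach to the extubation or to the anesthesia. On either parsing the anesthesia condition still governs. Only by reading the ICU as a free-standing alternative, which strains the sentence, does an ICU patient without anesthesia qualify.

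| Patient | Study Design and objective | Inclusion criterion as worded |
|---|---|---|
| Extubated in OR or other anesthesia location after anesthesia | in | in |
| Extubated in ICU after surgery under anesthesia | in | in |
| Extubated in ICU after critical illness, no anesthesia | in | not in |

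Neither exclusion criterion removes the third patient, so the conflict comes only from the missing limb.

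**2. The protocol's own figure.** Inputs from the sample-size section: incidence p = 0.08, total 95% confidence interval width w = 0.02.

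n = 1.96² × p(1 − p) / (w/2)² = 3.8415 × 0.0736 / 0.0001 = 2,827.3, against 2,827 stated. It reproduces. Allowing for 5% missing, 2,827 / 0.95 = 2,976, which the target of 3,000 covers. The planned half-width is 1.96 × √(0.0736 / 2,827) = 0.010, or 1.0 percentage point.

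**3. Illustration of the possible shift.** The protocol gives neither the share f of the sample in the omitted group nor its incidence q. Assume f = 10-30%, q = 12-20%, an overall incidence of 8%, and every centre reading the criterion literally. The incidence in the remainder is

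p_rem = (0.08 − f·q) / (1 − f).

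| f | q | p_rem | Shift from 8% |
|---|---|---|---|
| 0.10 | 0.12 | 0.068/0.90 = 7.6% | 0.4 points |
| 0.10 | 0.20 | 0.060/0.90 = 6.7% | 1.3 points |
| 0.20 | 0.16 | 0.048/0.80 = 6.0% | 2.0 points |
| 0.30 | 0.12 | 0.044/0.70 = 6.3% | 1.7 points |
| 0.30 | 0.20 | 0.020/0.70 = 2.9% | 5.1 points |

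In the middle row the omitted group would carry 0.20 × 0.16 × 2,827 ≈ 90 of the 0.08 × 2,827 ≈ 226 expected events. The results only restate the assumed inputs. Here f must be the patients who never had anesthesia, who are a subset of the critically ill. If only some centres read the criterion literally, and case mix is otherwise similar, the pooled figure falls between p_rem and 8%.

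**The case against.** The best defence is that the rest of the document leaves little doubt about intent. Sites are told to screen all in-hospital extubations in the three settings. The ICU stream carries no anesthesia condition, and the life-support exclusion fits ICU care. Critical care investigators are included at each centre and research personnel are trained. Exclusions are logged for ICU and anesthesia patients as two groups, and OR-versus-ICU analyses are planned. The log and the interim look after ten centres could reveal divergent practice.

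Much of this stands. It shows what the sponsor wants, makes uniform misreading less likely and improves the chance of detection. It does not amend the criterion: screening finds only potentially eligible patients, and the criterion then decides.

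A reader might also infer more than the documents support:

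- **That half the target population is lost.** Critical illness is one of two named groups, but no share is given, and the objective's wording lets the groups overlap.
- **That the highest-risk group is lost.** This is plausible, but the protocol states no comparative OR and ICU incidence.
- **That nothing could be said about critical illness.** Critically ill patients ventilated in the ICU after anesthesia still qualify.
- **That centres have already diverged.** Nothing in the protocol shows this; the risk is conditional.

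**Conclusion.** The point holds as an internal inconsistency in the eligibility text. The criterion is wrong as written, because followed literally it drops a group that the Study Design and the primary objective set out to include. It needs correction, since no later analysis can recover patients who were not enrolled.

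The size cannot be derived from the protocol. Under the assumptions above, the remainder would have an incidence of 2.9-7.6% against 8% overall. The shift is below the planned 1.0-point half-width at the mild end and several times that half-width at the far end. The finding does not depend on these figures. Nor does it make 2,827 a wrong calculation: the open question is which population the incidence describes, and whether 8% is the right expectation for it.

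**What to change.** Reconcile the three passages. In the inclusion criterion, add *or after critical illness* directly after the anesthesia condition, and keep the three locations as places where the extubation occurs. Send a short clarification to every centre.

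For windows already completed, search the daily exclusion log for ICU patients rejected for lack of anesthesia. The protocol does not define that reason as a category, so the recorded reasons may have to be read individually. Report the affected centres, or repeat the primary estimate and the OR/ICU strata without them as a sensitivity analysis.

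Retrospective entry of missed patients is optional. It would need REB agreement, must respect the maximum of 50 patients per centre given under Study Centres, and should be flagged in the data. Outcomes such as the duration of desaturation within 60 minutes may be less well captured from records than prospectively.

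The cost is a one-phrase REB amendment, a memo to sites and a review of the log. If no centre rejected such patients, no extra analysis is needed.

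### The inclusion criterion names only general anesthesia and leaves out critical illness, which the study design and the primary objective both include

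*Protocol*

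**What the plan says.** Three places in the protocol state who is being studied.

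- **Study Design:** "patients who require extubation after general anesthesia or after critical illness", in the OR, out-of-OR anesthesia locations or the ICU.
- **Sample Size and Number of Study Centres**, quoting the primary objective: "to estimate the incidence of immediate complications related to extubation in adult patients after general anesthesia and/or after critical illness".
- **Inclusion Criteria**, the only inclusion rule: adult extubations, both first and repeat, "after general anesthesia in the OR, out of OR anesthesia location or ICU during the specified enrollment window will be included".

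The first two name two routes into the study. The third names one, followed by the same three locations as in the Study Design.

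Other text bears on intent. Under Patients, screening covers "screening all inhospital extubations occurring in the ORs, out of OR anesthesia locations and ICUs during the enrollment window", and a separate sentence adds: "Potentially eligible patients in the ICU will be identified by screening ICU census lists". Extubation at withdrawal of life support is an exclusion. Data Quality and Security asks for a daily reason for non-inclusion, for ICU patients as well as for those having general anesthesia. OR versus ICU is an analysis stratum under Statistical Analysis, and a marked OR/ICU difference can prompt a change of sample size or centre mix under Interim Analysis.

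**The concern.** Eligibility is decided locally from the inclusion criterion, not from the Study Design paragraph. On the natural reading, the general-anesthesia condition governs all three locations, and the ICU is only a place where such a patient may be extubated. A patient intubated for pneumonia, which is the Rationale's own example of critical illness, then fails the only inclusion rule.

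At least 60 hospitals worldwide will apply the sentence. Some may log medical ICU patients as exclusions while others enrol them. The ICU case mix would then differ between centres for a reason unrelated to practice. That would carry into the overall incidence, the OR versus ICU stratum, the interim OR/ICU comparison from the first 10 centres, and the risk-factor models. It would also weaken the argument for the consent waiver, which rests on including consecutive patients so that the estimate is unbiased. Adding centres until 3,000 patients are reached restores the number but not the missing group, and each centre has only a two-week window.

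**Working it through.** **1. The passages side by side**

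| Place | General anesthesia | Critical illness | Locations |
|---|---|---|---|
| Study Design | yes | yes | OR, out-of-OR, ICU |
| Primary objective | yes | yes | not listed |
| Inclusion Criteria | yes | **absent** | OR, out-of-OR, ICU |

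The locations agree between the first and third rows. Only the second route into the study has dropped out.

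**2. Does the stated sample size depend on this?**

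Inputs from the sample size section: expected incidence p = 0.08; 95% confidence interval of total width 2 points, so half-width h = 0.01.

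n = 1.96² × p(1 − p) / h² = 1.96² × 0.08 × 0.92 / 0.01² ≈ 2,827, as stated.

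Allowing for 5% missing outcomes: 2,827 / 0.95 ≈ 2,976, which the protocol rounds up to 3,000.

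No input is an ICU or critical-illness share, so the wording conflict leaves 2,827 as it is.

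**3. Possible shift in the incidence (illustration only)**

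The protocol gives neither the ICU share nor the risk by location. Assumed: OR risk 5%, ICU risk 15% for all ICU patients, 30% of records from the ICU.

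- Everyone included: 0.70 × 5% + 0.30 × 15% = 3.5% + 4.5% = 8.0%. These inputs combine to exactly the protocol's expected figure.
- Literal reading at every centre, half of the ICU records postoperative and so still eligible: (0.70 × 5% + 0.15 × 15%) / 0.85 = 5.75% / 0.85 = 6.8%. Shift: about 1.2 points.
- Literal reading at every centre, no ICU record postoperative: 5.0%. Shift: 3 points, the upper limit under these inputs.
- Half of the ICU records postoperative, but only half of otherwise similar centres reading literally: 7.5% of records are lost, giving (3.5% + 0.225 × 15%) / 0.925 = 6.875% / 0.925 = 7.4%. Shift: about 0.6 points.

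The yardstick is the planned half-width of 1 point. Depending on the assumptions, the shift falls below or above it.

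**The case against.** The strongest reply is that the protocol, read as a whole, plainly intends to include critically ill patients. ICUs are screened from their own census lists, separately from the general-anesthesia lists. Withdrawal of life support is an exclusion that mainly concerns the critically ill. OR versus ICU is both a stratum and an interim check. The sentence can also be parsed so that the anesthesia condition attaches to the OR alone and the ICU stands by itself. Training is planned for all research personnel, each centre has anesthesia and critical care investigators, and the daily log of reasons for non-inclusion would record a centre that excluded such patients.

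Much of this stands. The omission is a drafting conflict, not a decision to exclude, and the safeguards make unnoticed divergence less likely. But screening only finds candidates, and the criterion decides on them. Each of the supporting passages is also compatible with an ICU group limited to postoperative patients, so a site could comply with all of them and still exclude medical ICU patients. The log would show the problem but not bring back patients from a closed window.

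Three stronger readings are tempting and not supported:

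- **That half of the study population is excluded.** Critical illness is one of two named populations. No share is given anywhere.
- **That the incidence would fall by 3 points.** This needs every centre to read literally and no ICU patient to be postoperative. Patients extubated in the ICU after general anesthesia remain eligible on any reading.
- **That post-anesthesia care unit extubations are wrongly left out.** That unit appears only among examples of centre descriptors. Study Design, screening and inclusion consistently name the same three locations, so there is no contradiction in eligibility to repair.

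**Conclusion.** The inclusion criterion conflicts with the population in the Study Design and in the primary objective. Taken literally, it shuts out ICU patients ventilated for critical illness without general anesthesia. The intent to include them is clear from the rest of the protocol but does not override the operative sentence.

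The risk is inconsistent enrolment across at least 60 centres, and hence a case mix that varies by centre in the main estimates. That this would happen is a possibility, not a certainty. The sample size is unaffected. In the illustration, the shift runs from about 0.6 points (half of centres literal, half of ICU records postoperative) through about 1.2 points (all centres literal) to at most 3 points (all centres literal, no postoperative ICU records). All three rest on assumed risks of 5% and 15% and an assumed 30% ICU share, with the same risk for postoperative and medical ICU patients. The contradiction itself rests on none of these figures.

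**What to change.** Reconcile the passages by adding the critical-illness alternative, in the Study Design's own words, directly after the reference to general anesthesia in the inclusion criterion. Keep the parenthesis that covers index extubations and re-extubations, and keep the three existing locations. No change for the post-anesthesia care unit is needed.

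The cost is a few words in one sentence, the amendment handling that each centre's ethics board requires, and a note to sites. Because enrollment windows run from January 2025 to December 2026, centres that have already finished should have their exclusion logs checked for ICU patients left out because they had not had general anesthesia, and the number should be reported. The sample size does not need to be recalculated.
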